8.1.2 Serious Adverse Events (SAEs)

Each AE will be assessed to determine whether it is serious or non-serious. (NOTE: The term serious is not synonymous with severity, which may be used to describe the intensity of an event experienced by the subject). A SAE is an AE that:

- 1) Led to a death; or
- 2) Led to serious deterioration in the health of the subject, that either resulted in:
 - a) A life-threatening illness or injury;
 - b) A permanent impairment of a body structure or a body function;
 - c) In-patient or prolonged existing hospitalization; or
 - d) Medical or surgical intervention to prevent life-threatening illness or injury or permanent impairment to a body structure or a body function
- 3) Led to fetal distress, fetal death or a congenital abnormality or birth defect.

Note: Planned hospitalization for a pre-existing conditions or procedures required by this study (including subsequent re-interventions assessed in study endpoints), without serious deterioration in health, are not considered SAEs.

To report an SAE, an event must first meet the protocol definition of an AE as described in section 8.1.

8.2 Severity of Adverse Events

Each AE should be assessed for its severity, or the intensity of an event, experienced by the subject according to the criteria below.

- *Mild:* Awareness of a sign or symptom that does not interfere with the subject's activity or is transient and is resolved without treatment or additional sequelae.
- *Moderate:* Interferes with the subject's usual activity and/or requires additional intervention and/or treatment, and may have additional sequelae.
- *Severe:* Symptom(s) causing severe discomfort to the subject and/or significant impact on the subject's usual activity. Additional intervention and or treatment are necessary. Additional sequelae occur.

IB/X\RRI

8.3 Relationship of Adverse Event to Device(s)/Procedure

Investigators will assess each AE for its relationship to the device or procedure. The following categories should be used for assigning the certainty of the relatedness:

- *Definitely Related:* An AE is definitely related if it is obvious, certain or there is little doubt regarding the relationship.
- *Possibly Related:* An AE is possibly related if it is capable of being related but relatively unlikely.
- *Not Related:* An AE is not related if it is determined that there is no plausible association.

Potential adverse events which may be associated with peripheral balloon dilatation with the UltraScore balloon are found in the IFU.

8.4 Reporting of Events

All AEs determined to be related to the device/procedure, should be recorded on the appropriate eCRF.

It is the responsibility of the Investigator to notify the IRB of applicable AEs in accordance with the governing IRB requirements.

See section 11.7 for all study reporting requirements.

8.5 Subject Death

Subject death, for any reason during the study, must be reported to the Sponsor within one (1) working day of the investigational site becoming aware of the event. Notification of a subject death should be done by email, telephone call, or fax.

Notification of death must include a brief statement of the pertinent details. All available medical records related to the subject's death must be maintained.

8.6 Device Deficiencies

The Investigator will record any device deficiencies on the appropriate eCRF. A device deficiency has occurred if a study device used in the study procedure failed to meet its performance specifications whether due to mechanical failure, malfunction, or defect. Device deficiencies also include errors and inadequate labeling.

This applies to:

- Study devices used in the subject; or
- Study devices in which the catheter package was opened, but the device was not used for catheterizing the subject; or
- Study devices with which insertion attempts were made, but the study device was not used in the subject.

All mechanical failures, malfunctions, and defects of the study devices will be recorded on the appropriate eCRF page and will be promptly reported to the Sponsor. The device(s) should be returned to the Sponsor as outlined in the sites regulatory binder.

If the device deficiency was associated with an AE, the reporting provisions for AEs apply.

Any device deficiency that did not lead to an AE but could have led to one, if suitable action had not been taken, if intervention had not been made or if circumstances had been less fortunate must be reported to the Sponsor within one (1) working day of the event per Section 8.4.

It is the responsibility of the Investigator to notify the IRB of such device deficiencies in accordance with the IRB and/or the Competent Authority's local regulations.

9 DATA COLLECTION AND RECORD MAINTENANCE

The Investigator is responsible for ensuring the complete and accurate recording of patient study data in the appropriate sections of the source documentation and eCRFs provided. The monitor will ensure the accuracy of data recording at each investigational site by comparing recorded data to supporting source documents during periodic site visits. Adherence to proper recording of information as well as ensuring that corrections are being made will also be addressed during these periodic visits.

9.1 Electronic Data Capture (EDC)

The Investigator is responsible for ensuring the completeness and accuracy of all study documentation. All Clinical study data will be recorded in eCRFs provided to the site.

9.2 Record Retention

The Investigator shall retain all study records for a period of two years after the later of the following two dates: the date on which the study is terminated or is completed.

10 MONITORING AND AUDITING

The study monitors are designated as agents of Bard and are assigned to oversee the conduct and progress of the study and to be the principal communication link between Bard and the Investigator. The study monitors may assist in pre-qualifying potential investigational sites. The study monitors will periodically conduct on-site inspection and monitoring of sites and records, to ensure continued compliance with this protocol and adequacy of the Investigator and the site to conduct the study.

Sites may also be subject to quality assurance audit by personnel of Bard (and its affiliates). It is important that the Investigator(s) and the relevant investigational site personnel are available during the monitoring visits and possible audits and that sufficient time is devoted to the process.

10.1 Site Initiation Visits

Before the study begins, the study monitors may visit the investigational site or conduct an online meeting (e.g., WebEx) to review with the Investigator(s) and staff the provisions and proper conduct of this study. This visit will include a detailed review of this protocol, verification that all necessary documents are on file at the investigational site and confirmation of IRB approvals.

10.2 Ongoing Monitoring Visits

The study monitor will conduct periodic on-site or remote inspection and monitoring of the investigational site and records to ensure compliance with this protocol.

The study monitor will maintain personal contact with the Investigator and staff throughout the study by telephone, e-mail, fax, mail and on-site visits. The study monitor will confirm that the ICF to be used is the version approved by the IRB and verify that all necessary documents are on file at the investigational site.

10.3 Final Monitoring Visit

At the completion of the study, the study monitor will conduct a final visit. The purpose of this visit is to collect all outstanding study data documents, confirm that the Investigator's files are accurate and complete, review the record retention requirements with the Investigator, and ensure that all applicable requirements for closure of the study are met. The actions and observations made at this visit will be recorded and filed.

11 ADMINISTRATIVE REQUIREMENTS

11.1 Investigator and Site Selection

The Investigator must be of good standing as an Investigator and knowledgeable in relevant areas of clinical research to ensure adherence to the requirements of this protocol, including the protection of human subjects. Other site personnel must have appropriate research experience and infrastructure to ensure adherence to this protocol and enrollment of sufficient numbers of evaluable study subjects. The curriculum vitae (CV) of the Investigator(s), Sub-Investigator(s) and Study Coordinator(s) will be maintained in Bard's files as documentation of qualification by training and experience. Federal databases will be searched to ensure that the Investigator(s) and/or the site are not prohibited from engaging in federally-sponsored clinical research.

The Principal Investigator and Sub-Investigator(s) will sign the signature pages of this protocol, agreeing to comply with all applicable government regulations and the requirements of this study as per the Clinical Study Agreement (CSA).

11.2 Training

Each investigator and appropriate site personnel will be trained on this protocol and study procedures. All training will be documented and filed at the investigational site and with Bard. The Investigators participating in this study will have had substantial experience previously performing endovascular procedures with scoring balloons (including VascuTrak), standard PTA, and other adjunctive endovascular procedures (e.g., DCB PTA, atherectomy, stent and stent graft procedures). Specific training on the UltraScoreTM Focused Force PTA balloon will be completed during the initiation visit.

11.3 Ethical and Regulatory Considerations

The Investigator must provide Bard with written documentation of IRB approval prior to the study being initiated. The IRB must give written renewal of the original approval at least annually to continue the study. A copy of each written renewal must be provided to Bard.

11.4 Informed Consent and National Privacy Laws

Prior to any study procedure, the Investigator (or designee) must explain to each subject in layman's terms, the nature of the study, its purpose, expected duration, and the risks and benefits of participation. Also, subjects will be informed of uses and disclosures of their medical information for research purposes, and their rights to access information about them. All applicable national privacy laws (e.g., HIPAA) will be followed. The subjects must be informed of their right to withdraw from the study at any time and for any reason without sanction, penalty, or loss of benefits to which they are otherwise entitled, and that withdrawal from the study will not jeopardize their future medical care.

After this explanation and before any study procedure is conducted, and before entering the study, the subject must voluntarily provide consent. The subject will receive a copy of his/her signed ICF.

11.4.1 Confidentiality

All information and data sent to the Sponsor or its designees that constitutes protected health information of study subjects will be considered confidential. All data used in the analysis and reporting of this study will be used in a manner without identifiable reference to the subject. The Investigator consents to visits by personnel of Bard and its affiliates or designees.

11.5 Deviations from Protocol and Medical Emergencies

The study will be conducted as described in this protocol. Any deviations from this protocol must be documented by the Investigator. If an emergency situation arises in which the safety and welfare of a subject may require immediate alternative intervention, the Investigator should act in the best interest of the subject. Bard and the site's IRB must be notified immediately if this occurs followed by written confirmation that describes the emergency action and outcomes.

11.6 Required Documents

An Investigator may not screen or enroll subjects until authorized to do so by Bard. At a minimum, the following documentation must be received by Bard prior to the commencement of study activities:

- Signed and executed Non-Disclosure Agreement (NDA) by PI and appropriate party at Bard;
- CVs, signed and dated within 2 years of study start for the PI;
- CVs for Study Coordinator(s);
- Signed Clinical Study Agreement (CSA) by PI (or designee);
- Signed "Protocol Signature Page" by PI;
- Signed "Financial Disclosure Statement" by PI;
- Written approval from the IRB of both the protocol and ICF.

11.7 Reporting Requirements

The Investigator must promptly report to Bard all progress and final reports and any withdrawal of IRB approval at the investigational site. At a minimum, the Investigator shall inform Bard of the following events according to the notification timelines below:

Event/Report Type:	Notification to:	Time to Notification:
Device-related AEs/SAEs	Bard and IRB (as applicable)	As soon as possible, but no later than one (1) working day after investigator awareness and per local IRB requirements.
Procedure-related AEs / SAEs	Bard and IRB (as applicable)	As soon as possible and per local IRB requirements.
Subject Death Bard and IRB		As soon as possible, but no later than one (1) working day after investigator awareness and per local IRB requirements. Relevant documentation to be submitted to the Sponsor no later than three (3) working days (See Section 8.5).
Device Deficiencies	Bard and IRB (as applicable)	As soon as possible. The device(s) should be returned to Bard. Any device deficiency that did not lead to an AE but could have led to an SADE, if suitable action had not been taken, if intervention had not been made or if circumstances had been less fortunate must be reported to the Sponsor within one (1) working day of the event.
(major*) Bard and IRB		As soon as possible, but in no event later than five (5) working days after emergency occurs (see Section 11.5).
Withdrawal of IRB approval	Bard	Immediately by telephone followed by a copy of the notification within five (5) working days.
Study progress report	Bard and IRB	At regular intervals or annually
Failure to obtain ICF	Bard	Within five (5) working days.
Final report	Bard	Within three (3) months of study completion

*Major protocol deviations are defined as those that occur to protect the life or physical well-being of a subject in an emergency, or those that may affect the scientific soundness of the study, or the rights, safety or welfare of human subjects.

11.8 Publication Policy

At the conclusion of this study, an article may be prepared for publication in a reputable scientific journal. The publication of the principal results from any single-center experience within the study is not allowed until the preparation and publication of the

multicenter results. A description of this study will be available on http://www.clinicaltrials.gov, as required by U.S. law.

11.9 Termination of Study

Bard reserves the right to suspend enrollment or terminate the study at any time as set forth in the CSA. Written notice will be provided in advance of such termination. Bard may suspend enrollment or terminate the patient study at a specific investigational site for reasons including, but not limited to, inadequate data collection, low subject enrollment rate, achievement of the total enrollment, or non-compliance with this protocol or other clinical research requirements.

13 APPENDICES

Abbreviation/Acronym	Definition		
AE	Adverse Event		
ASA	Aspirin		
CFR	Code of Federal Regulations		
CSA	Clinical Study Agreement		
СТО	Chronic Total Occlusion		
CV	Curriculum Vitae		
eCRF	Electronic Case Report Form		
EDC	Electronic Data Capture		
FDA	Food and Drug Administration		
GCP	Good Clinical Practices		
HIPAA	The Health Insurance Portability and Accountability Act		
ICF	Informed Consent Form		
IFU	Instructions for Use		
IRB	Institutional Review Board		
LTF	Lost to Follow-up		
MM	Medical Monitor		
NDA	Non-Disclosure Agreement		
PI	Principal Investigator		
РТА	Percutaneous Transluminal Angioplasty		
SAE	Serious Adverse Event		
US	United States		

13.1 Appendix A – Abbreviations and Acronyms

13.2 Appendix B – Time and Events Schedule

	Screening / Index Procedure / Discharge	30 Days (±7 days)	6 Months (±30 days)	12 Months (±30 days)
Informed Consent	\checkmark			
Demographics / Medical History	\checkmark			
Physical Examination	\checkmark			
Rutherford (Category and Grade)	\checkmark	✓	~	~
Resting ABI (Treated Limb only)	✓	✓	✓	~
Anticoagulation/Anti-platelets	✓	~	✓	✓
Eligibility Criteria	✓			
Angiographic Image Collection	✓			
Duplex Ultrasound§		~	✓	~
TLR Assessment		~	~	~
Adverse Event Assessment	\checkmark	~	~	✓

§ATK subjects only

		7.3.2	Assessment of Secondary Endpoints for subjects with DCB used baseline	at 4
		7.3.3	Assessment of death for subjects with DCB used at baseline eithe before or after ultrascore	r 4
8	Statisti	ical Analy	ses of Adverse Events and Device Deficiencies 1	4
	8.1	Adverse	Events (AEs) 1	4
	8.2	Device D	Deficiencies 1	4
9	Statisti Requir	ical Analy rements	vses of Baseline Examination, Other Analyses and Reporting	5
	9.1	Demogra Intervent	phics, Medical History, Risk Factors and Previous Target lesion ions1	5
	9.2	Relevant	Medication 1	5
	9.3	Target Lo	esion Characteristics (e.g. location, type) 1	5
	9.4	Procedur of inflatio	e Details (e.g. duration, inflation times, inflation pressures, number ons to efface/dilate the target lesion) 1	6
	9.5	Adjuncti	ve Therapies Before and After UltraScore Use 1	6

	9.6	Follow-up Period
	9.7	Subjects Dispositions
	9.8	Protocol Deviations
10	IVUS	Sub-Study
	10.1	Provisions17
	10.2	Endpoints
11	SAP R	evision History

1 Introduction

This document provides details of the statistical analysis plan (SAP) for the C.R. Bard, Inc. protocol BPV-16-001 (ULTRASCORETM PTA Balloon Study). This study is being done to provide physicians with real world data on the outcomes of use of the UltraScoreTM Focused Force PTA balloon, including optimal PTA results and long-term freedom from clinical target lesion revascularization (TLR), major amputation, and patency. For this study, optimal PTA results are those where \leq 30% residual stenosis remains after use of the UltraScoreTM Focused Force PTA balloon.

Follow-up for all treated subjects will be performed at hospital discharge, 30 days, and 6 and 12 months post-index procedure. Endpoint analysis will occur when all subjects have completed the 12 months follow up.

The statistical methods described here are based on the analyses proposed in the ULTRASCORETM PTA Balloon Study protocol issued on June 21, 2018, Version 2.0. All data processing, summarization, and analyses will be performed using Statistical Analysis System (SAS), Version 9.4 or higher.

1.1 Changes from Protocol

No changes from the protocol.

2 Study Objective and Endpoints

2.1 Study Objective

The objective of this study is to assess the clinical use of the Bard[®] UltraScore[™] Focused Force PTA balloon in a heterogeneous patient population in a real world, on-label clinical application.

2.2 Study Endpoints

2.2.1 Primary Endpoints

Primary endpoints are:

- Achieve optimal PTA results (≤30% residual stenosis, without major flow limiting dissection)
- Achieve technical success of use where the UltraScoreTM Focused Force PTA balloon is delivered to the target lesion and inflated without movement

2.2.2 Secondary Endpoints

The following secondary endpoints will be analyzed at the index procedure or through 12 months at these time points: 30 days, 6 months, and 12 months.

After UltraScore[™] Focused Force PTA balloon:

• Rate of bail-out stenting due to dissection

Through follow-up (at 30 days, and 6 and 12 months):

• Freedom from Target Lesion Revascularization (TLR)

- Freedom from major amputation (above the ankle)
- Improved clinical measures from baseline (ABI, Rutherford)
- Primary patency for ATK subjects only (as measured by DUS core lab)

3 Study Design

3.1 Overview

This study is a prospective, multi-center, single-arm, real-world study in the United States assessing the clinical use of the UltraScoreTM Focused Force PTA balloon. Treated subjects will be followed for 12 months post-index procedure. A duplex ultrasound (DUS) will be done at 30 days, and 6 and 12 months post-index procedure for ATK subjects. Otherwise, there are no additional treatments or exams that are required to take place within this study. There will be minimal patient activities that will be conducted for data collection purposes for this study in addition to routine standard of care procedures.

3.2 Study Population

Male or non-pregnant female ≥ 21 years of age with an expected lifespan sufficient to allow for completion of all study procedures. Eligible subjects will have a stenotic lesion of the SFA, popliteal, or infra-popliteal arteries. ATK subjects will be those that have a lesion of the SFA or popliteal artery. BTK subjects will be those that have a lesion in the infra-popliteal arteries (posterior tibial, anterior tibial or peroneal arteries)

3.3 Sample Size Consideration

There is no formal statistical hypothesis for this study. This study will enroll up to a maximum 350 subjects at approximately 45 sites. This will allow for approximately 175 subjects in an above the knee (ATK) cohort and 175 subjects in a below the knee (BTK) cohort. No site will be allowed to enroll more than 20% of the overall number of subjects to ensure the study be reasonably well balanced. The sample size is based on potential adequacy of data to meet the study objectives; it is not based on any statistical consideration.

3.4 Study Procedure

All subjects will undergo a clinical evaluation at screening (prior to index procedure); after consent is voluntarily obtained, study subjects will be treated with the UltraScoreTM Focused Force PTA balloon per the site's standard of care and adhering to the IFU. Examinations, evaluations, procedural preparation, angiography, treatment and hospital discharge procedures will be conducted per the study site's standard of care.

Investigators are able to treat One (1) lesion per patient in this study. If a subject has multiple eligible lesions, the investigator may use his or her medical judgment as to which becomes the study target lesion. Standard of care treatment of non-target lesions is allowed.

Subjects with treated ATK lesions will undergo clinical evaluations with a Duplex Ultrasound (DUS) performed at 30 days, 6 and 12 months post-index procedure.

Subjects with treated BTK lesions will undergo clinical evaluations performed at 30 days, and 6 and 12 months post-index procedure. DUS is not required for subjects with a treated BTK lesion for this study.

Lesions that cross from ATK to BTK may not be treated as the study target lesion. Diffuse lesions will be considered separate lesions if there is 2 cm of healthy tissue between lesions.

Angiographic imaging of the target lesion is captured at Baseline cine-run, Pre-UltraScore[™] adjunctive treatment cine-run (if performed), UltraScore[™] balloon inflation(s), Post UltraScore[™] balloon inflation(s) cine run, and Post UltraScore[™] adjunctive treatment cine-run (if performed). Angiographic imaging is also done at Re-Intervention visit. Major flow limiting dissections are collected and reporting is restricted to grades D, E, and F per the National Heart, Lung, and Blood Institute (NHLBI).

Adjunctive treatment of the target lesion before or after use of the UltraScore[™] balloon as part of standard care procedures is allowed. Bail out stenting and stenting of non-study lesions is acceptable at any time.

Collection and reporting of AEs/SAEs will be limited to those events that are device and/or procedure related and reporting will begin immediately following subject enrollment, during the index procedure.

If an angiographically acceptable result cannot be obtained after two inflations of the UltraScoreTM balloon (>30% residual stenosis), the subject should be considered a treatment failure.

An overview of the study visit schedules is shown in Table 1, which summarizes the schedule for subject treatment and evaluation.

Table 1: Follow-up Schedule a	nd Testing Requirements fo	r Enrolled Subjects
ruore in ronow up senedure u	ita Testing Requirements io	i Emoned Subjeets

	Screening / Index Procedure / Discharge	30 Days (±7 days)	6 Months (±30 days)	12 Months (±30 days)
Informed Consent	\checkmark			
Demographics / Medical History	\checkmark			
Physical Examination (Clinical Assessments)	\checkmark			
Rutherford (Category and Grade)	\checkmark	~	\checkmark	~
Resting ABI (Treated Limb only)	\checkmark	~	\checkmark	~
Anticoagulation/Anti-platelets	\checkmark	~	\checkmark	~
Eligibility Criteria	\checkmark			
Angiographic Image Collection	\checkmark			
Duplex Ultrasound§		\checkmark	\checkmark	\checkmark
TLR Assessment*		\checkmark	\checkmark	\checkmark
Adverse Event Assessment	\checkmark	\checkmark	\checkmark	\checkmark

§ATK subjects only

*Collect angiographic images for TLR/TVR

4 Analysis Set

Enrolled: All subjects who have signed the Informed Consent Form (ICF) and the UltraScoreTM balloon was introduced into the subject.

Intent-to-Treat (ITT): All enrolled subjects who have signed the ICF and were treated with the study device.

There is no formal statistical hypothesis for this study. Baseline characteristics, demographics, primary endpoints, secondary endpoints, other analyses and subgroup analyses will be based on the ITT population.

5 Statistical Analysis of the Primary Endpoints

The proportion of subjects with optimal PTA results and technical success will be reported with frequency counts, percentages and 95% confidence intervals (CI) for the percentages from exact binomial test.

5.1 To Achieve Optimal PTA Results (≤30% residual stenosis, without major flow limiting dissection)

The residual stenosis (Interpolated %DS) and major flow limiting dissection (Dissection) will be used from the Angio Core Lab CRF page (Image Findings-After UltraScore[™] Balloon QVA). If Angio Core Lab data is missing use the site data (site reported residual stenosis after inflations (%) from the Study Device CRF page and flow limiting dissection (D to F) from the Procedure Overview CRF page).

An optimal PTA result will be analyzed by subject as a binary endpoint based on the following definition:

- Not Evaluable: Subject has missing data for the residual stenosis and major flow limiting dissection; or it has success for one component and one component is missing.
- Failure: Subject has a failure event if residual stenosis after 2 inflations (%): is > 30% or if there is a major flow limiting dissection (D to F) as recorded from angio core lab. If angio data is missing use site data.
- Success: Subject has a no failure event in both the components and is evaluable.

The two-sided 95% CI will be provided for ATK, BTK and All UltraScore[™] subjects based on the binomial proportion for the ITT population.

5.2 To Achieve Technical Success of Use where the UltraScore™ Focused Force PTA Balloon is Delivered to the Target Lesion and Inflated Without Movement

A technical success of device recorded from the Study Device Details CRF page will be analyzed by device and not by subject, as a binary endpoint based on the following definition:

Not Evaluable: Device has missing data for the question "Was the Device Delivered to the Target Lesion and Inflated without Movement?"

Failure: Device has a failure event if the device was not delivered to the target lesion and not inflated without movement (i.e. failure event if "Was the Device Delivered to the Target Lesion and Inflated without Movement?" = No). If one device has several inflations and at least one of them is a failure, then the device is considered as failure.

Success: Device has a no failure event and is evaluable.

The two-sided 95% CI will be provided for ATK, BTK and All UltraScore[™] subjects based on the binomial proportion for the ITT population.

6 Statistical Analysis of Secondary Endpoints

6.1 After UltraScore™ Focused Force PTA balloon: Rate of Bail-Out Stenting due to Dissection

Becton Dickinson and Company	Confidential	Page 10
Protocol BPV-16-001	Statistical Analysis Plan	Jan 12, 2022

After UltraScore[™] Focused Force PTA balloon, rate of bail-out stenting due to dissection will be reported with frequency counts, percentages and 95% CIs for the percentages from exact binomial test. Bail-out stenting due to dissection after UltraScore[™] Focused Force PTA balloon reported from the Procedure Overview CRF page will be used. It will be analyzed by subject as a binary endpoint based on the following definition:

Evaluable: All ITT subjects.

- Failure: Subject has a failure event if they have flow limiting dissection after UltraScore[™] use time point with bail-out stenting. Also, subject with flow limiting dissection at Index procedure with bail-out stenting are failures.
- Success: Subject does not have a flow limiting dissection or subject has a flow limiting dissection after UltraScore[™] use time point with no bail-out stenting. Subject has a no failure event and is evaluable.

The two-sided 95% CI will be provided for ATK, BTK and All UltraScore[™] subjects based on the binomial proportion for the ITT population.

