7.3 Data Analysis

The analysis population consists of all enrolled subjects who have signed the Informed Consent Form and have been treated with the study device.

Study endpoints will be summarized using descriptive statistics. Summary statistics for categorical variables will include frequency counts and percentages and for continuous variables mean, standard deviation, minimum, median and maximum.

Primary endpoints will be reported by rate and with a 95% confidence interval. The calculation of rates will be based on available data. Missing data will not be imputed.

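### SAP 5 reports technical success per subject and SAP 5.2 analyses it per device, and the exact binomial interval makes no allowance for several balloons in one subject

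*SAP*

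**What the plan says.** The opening of SAP 5 covers both primary endpoints: "The proportion of subjects with optimal PTA results and technical success will be reported with frequency counts, percentages and 95% confidence intervals", the intervals coming from the exact binomial method. SAP 5.1 then analyses optimal PTA result by subject. SAP 5.2 says that technical success "will be analyzed by device and not by subject, as a binary endpoint based on the following definition", and defines not evaluable, failure and success for a device. It also has a rule for repeated inflations: "If one device has several inflations and at least one of them is a failure, then the device is considered as failure". There is no matching rule from device to subject.

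Protocol 7.3 leaves the unit open: "Primary endpoints will be reported by rate and with a 95% confidence interval". SAP 1.1 declares "No changes from the protocol". SAP 4 defines its analysis sets by subjects only. SAP 7.2 applies methods similar to those of section 5 to the adjunctive-treatment subgroups, and SAP 7.3.1 reports the primary endpoints by site.

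**The concern.** Two sections of the SAP give different denominators for the same primary endpoint. Read literally, SAP 5 cannot be carried out for a subject with two balloons, one successful and one not, because nothing says how that subject counts.

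The second part is conditional. If the device is the unit and some subjects receive more than one UltraScore balloon, those balloons share a target lesion and a procedure. An exact binomial interval on pooled devices assumes independent outcomes, and the SAP names no other interval.

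The study is descriptive, so the rate and its interval are the primary result. What is at stake is how that rate and its precision are read, here and in the subgroup and by-site tables that inherit the method. The references in 5.2 to ATK, BTK and All UltraScore subjects are not part of the complaint. They name reporting cohorts, as SAP 8.2 does for device deficiencies.

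**Working it through.** **No figure to reproduce.** The documents state no expected rate, interval width, number of balloons per subject or within-subject correlation. Cohort sizes (about 175 ATK, 175 BTK, at most 350 in all) come from SAP 3.3. All other inputs below are assumptions.

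**Can a subject have more than one balloon?** The documents allow it without counting it.
- Specifying the device rather than the subject has an effect only if it happens.
- Protocol 8.6 foresees "Study devices with which insertion attempts were made, but the study device was not used in the subject".
- Each subject has one study lesion ("Investigators are able to treat One (1) lesion per patient in this study"), but that lesion can be long. SAP 3.4 says "Diffuse lesions will be considered separate lesions if there is 2 cm of healthy tissue between lesions", so disease with shorter gaps is one lesion. The eligibility lists (Protocol 5.1 and 5.2) set no length limit beyond the IFU.

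**Effect of the unit on the rate.** Assume 350 subjects, with 18 first-balloon failures each replaced successfully (exact 95% intervals):
- By subject, any failure counts as failure: 332/350 = 94.9% (92.0-96.9).
- By subject, any success counts as success: 350/350 = 100% (99.0-100).
- By device: 350/368 = 95.1% (92.4-97.1).
- By device, if 105 subjects have a second balloon and there are still 18 failures: 437/455 = 96.0% (93.8-97.6).

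**Denominators and design effect.** Assumed shares of subjects with 1/2/3 balloons: (a) 85/13/2%, (b) 70/25/5%, (c) 50/35/15%. Mean balloons per subject:
- (a) 0.85 + 0.26 + 0.06 = 1.17
- (b) 0.70 + 0.50 + 0.15 = 1.35
- (c) 0.50 + 0.70 + 0.45 = 1.65

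So 175 subjects give about 205, 236 or 289 devices. With m balloons per subject and within-subject correlation ICC, the design effect is 1 + ICC × (Σm²/Σm − 1). Here Σm²/Σm is 1.55/1.17 = 1.325, 2.15/1.35 = 1.593 and 3.25/1.65 = 1.970. At ICC 0.6 the design effects are 1.19, 1.36 and 1.58. At ICC 0.9 they are 1.29, 1.53 and 1.87.

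**Coverage of the nominal 95% exact interval on pooled devices.** Beta-binomial simulation, 10,000 runs per cell. Each entry is the range over n = 175 and 350 and true success 90, 95, 98 and 99%.

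| ICC | Mix (a) | Mix (b) | Mix (c) |
|---|---|---|---|
| 0.1 | 95.6-98.1% | 95.2-98.9% | 94.8-98.1% |
| 0.3 | 94.9-97.6% | 94.1-98.1% | 92.4-97.3% |
| 0.6 | 93.7-97.1% | 92.1-97.4% | 89.6-95.8% |
| 0.9 | 92.6-96.8% | 89.7-96.5% | 86.0-94.9% |

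The low ends come mainly from 90-95% success. At 99% success and n = 175, coverage is at least 94.9% in every cell.

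A simpler model gives the same picture. Let a share q of subjects have two balloons, so the design effect is 1 + ICC × 2q/(1 + q) (90 and 95% success, n = 175 and 350, 20,000 runs per cell):
- q = 10%, any ICC: coverage 93.8-97.1%.
- q = 50%, ICC 0.5: design effect 1.33, coverage 91.6-92.6%.
- q = 100%, ICC 1 (worst case): design effect 2.0, coverage 84.0-88.1%.

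**Mean width at 90% success, n = 175, exact against subject-clustered:** mix (a), ICC 0.3, 8.6 against 8.8 points; mix (b), ICC 0.6, 8.0 against 9.1; mix (c), ICC 0.9, 7.2 against 9.6.

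**Failed balloon simply replaced.** If 2, 5 or 10% of first balloons fail and each is replaced successfully, outcomes within a subject are negatively related. Exact coverage is then 99.1, 97.9 and 97.6% at n = 175, and 98.1, 96.4 and 98.0% at n = 350 (40,000 runs). The interval is somewhat too wide.

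**Does a clustered interval work?** A logit-scale cluster-robust interval (t with n − 1 df), with an exact interval on subjects when a cohort has no failures, covers 94.0-97.5% across mixes (a)-(c). At 99% success and n = 175, the fallback is needed in 6-17% of runs. At site size, 350/45 = 7.8 or about 8 subjects, it is conservative at 90-95% success. A subject-level bootstrap was not simulated.

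**The case against.** SAP 5.2 is the endpoint-specific section: it states the unit and excludes the alternative, whereas SAP 5 is a shared lead-in. This stands. An analyst would use devices, and a device rate needs no defence. The lead-in still contradicts it, and it is also where the exact method is named.

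The clustering argument rests on no documented count of balloons. This stands too. Protocol 8.6 concerns deficiency reporting and does not say that a second balloon follows, and the diffuse-lesion rule says nothing about balloon numbers. With one balloon per subject the two denominators coincide and the interval is right.

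The milder scenarios show little harm, replacement makes the interval conservative, and the direction of any error is unknown in advance. All of this is correct. It argues for an interval that holds in every case, since the data to compute it are already collected.

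Nothing is tested, and the protocol fixes no unit, so the SAP 1.1 statement is not contradicted. Both are true. They limit the consequence to the reported rate and its precision, which in a descriptive study is the primary result.

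Switching to subjects when there are no failures changes the unit depending on the data. That is a fair criticism, and it is met by writing the rule down beforehand.

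**Conclusion.** The point holds. SAP 5 and SAP 5.2 give different units for a primary endpoint, and nothing else in either document decides between them. With devices as the unit, the stated interval makes no allowance for several balloons in one subject.

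The wording conflict needs no assumption. The size of the interval problem does: it is negligible if repeat balloons are few or weakly correlated, material only if they are common and strongly correlated, and reversed if failed balloons are merely replaced. Confidence in its practical size is therefore moderate. The correction should be made, but it alters no test, threshold or sample size.

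**What to change.** State one unit in SAP 5 and 5.2.

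- **If device:** correct the SAP 5 sentence, report the numbers of devices and of subjects, and use a subject-clustered 95% interval (cluster-robust, or a subject-level bootstrap once its behaviour has been checked). Pre-specify that a cohort with no failures gets the exact interval on the number of subjects; for 175/175 the lower limit is 0.025^(1/175) = 97.9%, giving 97.9-100%.
- **If subject:** pre-state the device-to-subject rule, for example that every balloon must succeed, in line with the existing inflation-to-device rule, and keep the exact binomial interval.

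A supportive rate on the other unit is optional. Carry the chosen unit into SAP 7.2 and 7.3.1.

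The cost is a wording change, a dated SAP revision and a few lines of code on data already on the Study Device Details CRF page. The rate or interval may shift slightly. If nearly every subject has one balloon, nothing visible changes.
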